### 2.2. Secondary Objective(s)

The key secondary objectives of Study 2 are:

- To demonstrate that ZX008 0.2 mg/kg/day is superior to placebo as adjunctive therapy in the treatment of Dravet syndrome based on change in the frequency of convulsive seizures between baseline and T+M.
- To demonstrate that the ZX008 0.2 and 0.8 mg/kg/day dose groups are (independently) superior to placebo on the following endpoints:
  - The proportion of subjects who achieve a  $\geq 50\%$  reduction from baseline in convulsive seizure frequency.
  - The longest convulsive seizure-free interval.

Additional Secondary Objectives:

- To demonstrate that the ZX008 0.2 and 0.8 mg/kg/day dose groups are (independently) superior to placebo on the following endpoints:
  - The number of convulsive seizure-free days.
  - The proportion of subjects who achieve  $\geq 25\%$ , or  $\geq 75\%$ , or 100%, or near seizure-free (ie, at most 1 convulsive seizure) reductions from baseline in convulsive seizure frequency.
  - The change from baseline in non-convulsive seizure frequency.
  - The change from baseline in convulsive + non-convulsive seizure frequency
  - The incidence of rescue medication usage
  - The incidence of hospitalization to treat seizures
  - The incidence of status epilepticus.
- To demonstrate that the ZX008 0.2 and 0.8 mg/kg/day dose groups are (independently) superior to placebo on the following endpoints:
  - Clinical Global Impression – Improvement rating, as assessed by the principal investigator.
  - Clinical Global Impression – Improvement rating, as assessed by the parent/caregiver.
  - The change from baseline in the Quality of Life in Childhood Epilepsy (QOLCE) score.
  - The change from baseline in the Pediatric Quality of Life Inventory™ (PedsQL) score.
  - The change from baseline in the PedsQL Family Impact module score.
  - The change from baseline in the QoL of the parent/caregiver using the EQ-5D-5L scale.
  - The change from baseline in the affective symptoms of the parent/caregiver using the Hospital Anxiety and Depression Scale (HADS).

The safety objective of the Study 2 is:

- To compare the safety and tolerability of ZX008 0.2 and 0.8 mg/kg/day to placebo with regard to AEs, laboratory parameters, physical examination, neurological examination, vital signs (blood pressure, heart rate [HR], temperature, and respiratory rate), ECGs, ECHOs, and bodyweight. Cognitive function will be assessed using age-appropriate versions of the Brief Rating Inventory of Executive Function (BRIEF).

This document is confidential.

## Statistical Analysis Plan

Sponsor: Zogenix International Limited; Protocol No.: ZX008 Study 2 (ZX008-1501 and ZX008-1502)

---

### Pharmacokinetic Objective:

- The pharmacokinetic (PK) objective of Study 2 is:
- To characterize the PK of ZX008 0.2 and 0.8 mg/kg/day at steady state in subjects ages 2-6 years and >6-18 years with Dravet syndrome.

### Exploratory Objective

The exploratory objective of the Study 2 is:

- To compare the ZX008 0.2 and 0.8 mg/kg/day doses on primary, secondary, safety and PK endpoints.

### 2.3. Brief Description

Both Study 1501 and Study 1502 are multicenter, double-blind, parallel-group, placebo-controlled studies designed to assess the efficacy, safety, and PK of ZX008 when used as adjunctive therapy in pediatric and young adult subjects with Dravet syndrome. Study 1501 was conducted at approximately 30 study sites in North America; Study 1502 was conducted at approximately 30 study sites in Europe, Australia, and Japan. For Study 1502 Japan was added in 2019 whereas Europe and Australia started in 2015. Approximately 36 sites will contribute randomized subjects to Study 1502.

The expected study period of 22 weeks comprises a Baseline period (6 weeks), a Treatment period (14 weeks) (2 weeks titration + 12 weeks maintenance), and a Post Dosing visit 2 weeks after study completion or early termination.

Upon study completion, eligible subjects will be able to receive ZX008 in an open-label extension study for up to 1 additional year of treatment. There will be cardiac safety follow-up of 3 to 6 months after study drug discontinuation for early termination or for subjects who complete the study but do not enroll in the open-label extension study. Subjects from France, Germany and the Netherlands will have a cardiac safety follow-up visit approximately 24 months after the last dose of active study medication. Follow-up safety visit results will be reported separately.

Upon completion of the Baseline Period, subjects who qualify for the study will be randomized (1:1:1) in a double-blind manner to receive 1 of 2 doses of ZX008 (0.2 mg/kg/day, 0.8 mg/kg/day; 30mg/day maximum) or placebo. The randomization will be stratified by age (<6 years, ≥6 years) to ensure balance across treatment arms, with the target of 25% of subjects in each age group. Subjects will be assigned a randomization number by the IWR system upon confirmation that subject qualifies for enrollment in the Titration Period. Once a randomization number is assigned to a subject, the site will record the subject's initials and identification number on the corresponding study drug bottles. Each bottle will contain the assigned treatment (ZX008 0.2 mg/kg/day, ZX008 0.8 mg/kg/day, or placebo). ZX008 and placebo will be identical, thus rendering the study drug and placebo indistinguishable. The randomization scheme and block size for Studies 1501 and 1502 are the same, so combination of the data from the two studies will not skew the intended randomization into the three treatment groups.

Due to slow enrollment, Studies 1501 and 1502 were merged into a single dataset for analysis and reporting. The first 119 subjects randomized comprised Study 1, which was reported in September 2017. This analysis enabled an earlier determination of the benefit-risk profile of ZX008, to minimize the total subject exposures should the risk-benefit profile not be positive. The subsequent approximately 120 subjects to be randomized, comprise Study 2. Study 2 represents the cohort of subjects in Studies 1501 and 1502 whose data were not included in Study 1.

This document is confidential.

## Statistical Analysis Plan

Sponsor: Zogenix International Limited; Protocol No.: ZX008 Study 2 (ZX008-1501 and ZX008-1502)

---

Study 1501 and Study 1502 are being conducted in parallel with each study independently assigning treatments using randomized permuted blocks; thus, combining subjects from the two identically designed studies meant that 2 sets of randomized blocks were used, which had approximately the same effect as doubling the block size in a single study. Combining the first 120 randomized subjects from Study 1501 and Study 1502 to create Study 1 and Study 2 preserves the balance among the 3 treatment groups in each of Study 1 and Study 2, yielding approximately 40 subjects per arm, the number required to maintain full statistical power.

After the last of the subjects in Study 2 has either discontinued or completed treatment, the database will be locked for those subjects and Study 2 will be reported as per this SAP.

### 2.4. Subject Selection

The study population will be selected on the basis of the inclusion and exclusion criteria described in the protocol.

### 2.5. Determination of Sample Size

The sample sizes for Zogenix Studies 1501 and 1502 were calculated based on the results of two trials with stiripentol reported in the European Public Assessment Report (EPAR) for stiripentol (EMA, 2007). The stiripentol EPAR summarizes the results from two studies: STICLO France and STICLO Italy. In the stiripentol groups, the standard deviation (SD) of the percentage change in seizure frequency from baseline to month 2 was 42% in the French trial and 26% in the Italian trial. The analogous SDs for placebo groups were 38% and 62%. An SD of 50% was assumed for the primary analysis in Protocols 1501 and 1502 that compares ZX008 0.8 mg/kg/day to placebo on the change from baseline in seizure frequency. Using a two-sided test at the  $\alpha=0.05$  significance level, a sample size of 35 subjects per treatment group affords 90% power to detect a difference in mean change from baseline of 40 percentage points. Similar assumptions and calculations yielded a requirement for an additional 35 subjects in the 0.2 mg/kg/day ZX008 group. The total sample size for each study was therefore set at 105 subjects.

In December 2016 results from a double-blind, placebo-controlled Phase 3 study with Epidiolex® (cannabidiol) to treat seizures in Dravet syndrome were presented at the American Epilepsy Society Meeting (<http://ir.gwpharm.com/events.cfm>). In the Epidiolex study, active drug reduced seizures by 39% compared to a reduction of 13% in the placebo. Review of the data suggested that the standard deviation was relatively large, likely above 50% in both treatment groups. In consideration of this new data, the sample size was re-estimated for the ZX008 studies to assume a SD of 55%, higher than the previous estimate of 50%. Other assumptions in the sample size calculation remained unchanged. A sample size of approximately 120 subjects (40 per arm) affords 90% power to detect a difference in mean change from baseline of 40 percentage points with 55% SD. Considering the variability seen in the STILCO and Epidiolex trials, the sample size for Study 1 and Study 2 is set at 120 subjects, 40 per treatment arm. Note that the change in assumed SD was based entirely on data from external trials. Efficacy data from both Study 1501 and 1502 are still blinded and were not used in re-estimating the required sample size.

### 2.6. Treatment Assignment & Blinding

Subjects in Study 2 were originally in either Study 1501 or Study 1502. Upon completion of the Baseline Period, subjects who qualify for the study will be randomized (1:1:1) in a double-blind manner to receive 1 of 2 doses of ZX008 (0.2 mg/kg/day, 0.8 mg/kg/day; 30mg/day maximum) or placebo. The randomization was stratified by age (<6 years,  $\geq 6$  years) to ensure balance across treatment arms, with

This document is confidential.

## Statistical Analysis Plan

Sponsor: Zogenix International Limited; Protocol No.: ZX008 Study 2 (ZX008-1501 and ZX008-1502)

a target of  $\geq 25\%$  of subjects in each age group. Subjects were assigned a randomization number by IWR system upon confirmation that the subject qualified for enrollment in the Titration Period. Once a randomization number was assigned to a subject, the site recorded the subject's initials and identification number on the corresponding study drug bottles.

Each bottle contained the assigned treatment (ZX008 0.2 mg/kg/day, ZX008 0.8 mg/kg/day, or placebo). ZX008 and placebo were identical, thus rendering the study drug and placebo indistinguishable. The blinding scheme instituted for this study ensured that the volume of study medication taken could not be associated with the dose group, thus unblinding the study. This was achieved by random assignment of different concentrations of the ZX008 oral solution (1.25 mg/mL, 2.5 mg/mL, and/or 5 mg/mL) by the IVR/IWR system. The IWR system instructed site personnel to the volume of oral solution to be administered based on that subject's weight. (Dose was to be recalculated by the system once at the midpoint of the study.) During the Titration, Maintenance, and Taper/Transition Periods, the subjects and study personnel (investigators, clinical staff, personnel involved in data collection and analysis, the Medical Monitor, and the sponsor) were blinded to the treatment allocation and to the concentration of ZX008 oral solution.

Prior to database lock for Study 1 an unblinding plan was implemented. The purpose of unblinding plan was to provide specific information and guidance to the Clinical Development Team, Clinical Operations Team, Biostatistics, Project Management, and other functions regarding plans for unblinding key team members for analysis of Study 1 top-line data and final Tables, Listings, and Figures (TLFs). 'Unblinding' is defined as having access to subject-level data (i.e., subject data listings or the randomization codes) that provides information regarding randomized dose group, treatment effect, and safety. Access to aggregated data (ie, group-level tables and figures) does not constitute 'unblinding' and for the purposes of data cleaning and database lock, these individuals were still considered 'blinded'.

Personnel from the sponsor or any designee who became unblinded for the purposes of data cleaning and database lock for Study 1 did not participate in any decision-making regarding subjects' data for Study 2 to avoid any real or apparent bias in such decisions. Study 2 was to be completed by a blinded study team with personnel distinct from the unblinded team that worked on Study 1.

### 2.7. Administration of Study Medication

ZX008 is supplied as an oral solution in concentrations of 1.25, 2.5, and 5 mg/mL. Subjects were randomized to receive 1 of 2 doses of ZX008 (0.2 mg/kg/day, 0.8 mg/kg/day; maximum dose: 30 mg/day) or placebo. Placebo is identical in aspect and composition to ZX008 and is composed of identical ingredients used in the ZX008 formulation, except that it does not contain the active ingredient, fenfluramine hydrochloride.

Study medication was administered twice a day (BID) in equally divided doses with food.

- Treatment ARM A: ZX008 0.2 mg/kg/day
- Treatment ARM B: ZX008 0.8 mg/kg/day
- Treatment ARM C: Placebo

#### Treatment Periods:

#### Titration Period:

Study medication was administered as equal doses BID in the morning and in the evening approximately 12 hours apart, with food. Each dose should have been separated by a minimum of 8 hours and a

This document is confidential.

**Statistical Analysis Plan**

Sponsor: Zogenix International Limited; Protocol No.: ZX008 Study 2 (ZX008-1501 and ZX008-1502)

maximum of 12 hours. A missed dose of study medication was to be taken later up to 8 hours before the next scheduled dose; otherwise, the missed dose should not be given.

Administration of the Investigational Medicinal Product (IMP) was based on the randomized dose and subject's weight at Visit 3 (Day -1). At Visit 8 (Day 43), if the subject's weight changed  $\pm 25\%$  of the weight at Day-1, the IMP dose was recalculated. Subjects were dosed using the oral dosing syringe provided.

In order to maintain the blind across all dose groups and allow step titration to the high dose, the dose for each subject was titrated starting with a dose of ZX008 0.2 mg/kg/day (or placebo equivalent) BID. After 4 days at this dose level (Day 5), subjects randomized to the ZX008 0.8 mg/kg/day group increased their dose to 0.4 mg/kg/day while doses in the other two groups remained constant. On Day 9, the dose for the 0.8 mg/kg/day group increased to the target dose. The titration was expected to take a total of 14 days (Table 1). A new bottle of IMP was started by the subject at each level of the titration step.

Table 1: Titration Algorithm

Randomized Group	Titration Step 1 Study Day 1-4	Titration Step 2 Study Days 5-8	Titration Step 3 Study Days 9-14
ZX008 0.2 mg/kg/day	ZX008 0.2 mg/kg/day	ZX008 0.2 mg/kg/day	ZX008 0.2 mg/kg/day
ZX008 0.8 mg/kg/day	ZX008 0.2 mg/kg/day	ZX008 0.4 mg/kg/day	ZX008 0.8 mg/kg/day
Placebo	Placebo	Placebo	Placebo

Note: maximum daily dose of ZX008 is 30 mg.

**Maintenance Period:**

After completion of the Titration Period, subjects entered the Maintenance Period and continued to receive the randomized dose of ZX008 or placebo and be treated for an additional 12 weeks. Study medication continued to be administered BID in the morning and in the evening, approximately 12 hours apart, with food. Each dose was to be separated by a minimum of 8 hours and a maximum of 12 hours. A missed dose of study medication may have been taken later up to 8 hours before the next scheduled dose; otherwise, the missed dose was not to be given.

**Taper Period:**

Subjects who complete the Maintenance Period and were not continuing into the open-label extension study and subjects who discontinued from the study early were to be tapered off from study medication. Study medication was administered as equal doses BID in the morning and in the evening approximately 12 hours apart, with food. Each dose should have been separated by a minimum of 8 hours and a maximum of 12 hours. A missed dose of study medication may have been taken later up to 8 hours before the next scheduled dose; otherwise, the missed dose should not be given. IMP was administered using the oral dosing syringe provided.

In order to maintain the blind across all dose groups, all subjects who did not continue into the open-extension study participated in a dose-tapering procedure over the course of 8 days. On the first day of the tapering period subjects in the ZX008 0.8 mg/kg/day group decreased to a dose of ZX008 0.4 mg/kg/day BID (maximum 30mg/day). After 4 days at this dose level (Day 5), subjects randomized to the ZX008 0.8 mg/kg/day group decreased their dose to 0.2 mg/kg/day. Subjects in the ZX008 0.2 mg/kg/day group decreased their dose to placebo on the first day of tapering while doses in the placebo group remained constant throughout the tapering procedure. On Day 9, all subjects stopped taking study medication. The taper was expected to take a total of 8 days (Table 2). A new bottle of IMP was started by the subject at each level of the taper step.

Table 2. Taper Algorithm

Randomized Group	Taper Step 1 Day 1-4 after study completion or early termination	Taper Step 2 Days 5-8 after study completion or early termination

This document is confidential.

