**Transition Period:**

Subjects who completed the Maintenance Period and were continuing into the open-label extension study were to be transitioned from double-blind study medication to open-label ZX008 (Table 3). Study medication was administered as equal doses BID in the morning and in the evening approximately 12 hours apart, with food. Each dose should have been separated by a minimum of 8 hours and a maximum of 12 hours. A missed dose of study medication may have been taken later up to 8 hours before the next scheduled dose; otherwise, the missed dose should not be given. Study medication was administered using the oral dosing syringe provided.

All subjects entering the open-label extension study were transitioned from their blinded daily dose (placebo, 0.2 mg/kg/day, 0.8 mg/kg/day, or 30 mg/day) to the 0.2 mg/kg dose during the 2-week interval between Visits 12 and 13, without breaking the blind. The IWR system assigned two bottles of IMP to the subject, one for each step in the transition. A new bottle of IMP was started by the subject at each level of the transition step.

Table 3. Transition Algorithm

Dose Group in Double-Blind Study	Transition Step 1 Day 1-4 after Visit 12	Transition Step 2 Days 5-14 after Visit 12
ZX008 0.2 mg/kg/day	ZX008 0.2 mg/kg/day	ZX008 0.2 mg/kg/day
ZX008 0.8 mg/kg/day	ZX008 0.4 mg/kg/day	ZX008 0.2 mg/kg/day
Placebo	ZX008 0.2 mg/kg/day	ZX008 0.2 mg/kg/day
Note: maximum daily dose of ZX008 is 30 mg.		

Subjects who had been randomized to placebo increased their dose to 0.2 mg/kg/day beginning on Day 1 of the transition (the day following Visit 12.) Subjects who had been randomized to 0.2 mg/kg/day continued to receive that dose. Subjects who had been randomized to 0.8 mg/kg/day or were receiving the maximum dose of 30 mg/day decreased to a dose of ZX008 0.4 mg/kg/day, or a maximum of 30 mg/day. After 4 days at this dose level (Day 5), these subjects decreased their dose to 0.2 mg/kg/day. Subjects were to report to the clinic on Day 15 for enrollment into the open-label extension study.

Data from the Taper or Transition period will not be included towards the planned efficacy endpoints except where specified, but will be included in the safety analyses.

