**Statistical Analysis Plan**

Sponsor: Zogenix International Limited; Protocol No.: ZX008 Study 2 (ZX008-1501 and ZX008-1502)

Table 4: Schedule of Assessment (Continued)

Study Assessments	Baseline Period a			Titration + Maintenance Period								EOS/ ET b	Post-Dosing	Cardiac Follow-up
	Screening	2 (Phone)	Random- ization	Titration Period			Maintenance Period							
Visit Number	1		3		4, 5 (Phone)	6	7 (Phone)	8	9 (Phone)	10	11 (Phone)	12	13	14
Study Day	-42 to -41	-21	-1	1	4, 8	15	29	43	57	71	85	99	113	3-24 mo post dose
Clinical Global Impression - Improvement (assessed by parent/caregiver)						X		X		X		X		
Clinical Global Impression - Improvement (assessed by principal investigator)						X		X		X		X		
BRIEF			X					X				X		
QOLCE			X					X				X		
PedsQL			X					X				X		
EQ-5D-5L (QoL of parent/caregiver)			X					X				X		
HADS (Affect of parent/caregiver)			X					X				X		
Randomize subject			X											
First Day of Study Drug Administration				X										
Daily Diary Completion							X							
Concomitant Medication									X					
Adverse events							X							
Adverse events of special interest							X							X

AED=antiepileptic drug; BMI=body mass index; BRIEF=Behavior Rating Inventory of Executive Function; C=Colex, CBD=cannabidiol; D=Dispense; ECG=electrocardiogram; EOS=end of study; ET=early termination; EQ-5D-5L=standardized measure of health status; HADS=Hospital Anxiety and Depression Scale; PedsQL=Pediatric Quality of Life Inventory; QoL=quality of life; QOLCE=Quality of Life in Childhood Epilepsy; R=Review

- a: The Baseline Period is comprised of the initial screening for the study and the assessment of baseline seizure activity recorded daily in the diary.
- b: Subjects who are discontinued early and those who complete the study and choose not to enroll in the separate open-label extension will be tapered off study medication over an up to 2-week period.
- c: Follow-up ECG, ECHO, and physical examination if warranted will be performed 3-6 months after early termination, or for those subjects who complete the study but do not enter the open-label extension study

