#### **Missing Data Due to Dropouts:**

The issue of missing data has gained much attention subsequent to the National Academy of Science Report on the Treatment and Handling of Missing Data (NAS Report, 2010). Within the context of the studies, missing data arise from two sources: intermittent missing assessments (such as missing diary data), and as a result of dropouts prior to the end of the titration + maintenance periods.

In Study 1, only 2 (out of the 119) subjects had more than 7 days of missing diary data while on treatment (before dropout). The rates of dropout in the pivotal trials was 7.56% (9/119) in Study 1. Dropouts that are related to treatment response leave the possibility that the analysis of efficacy endpoints, which relies on assumptions of data being missing at random (MAR), may be violated. It is possible, though, that data may be missing not at random (MNAR). Differential dropouts leading to missing assessments may thus affect the inference on the primary endpoint.

The primary analysis method, in so far as it uses the convulsive seizure frequency averaged over the entire treatment period, in effect, assumes that a dropout would have followed the mean profile experienced up to that point in time when the subject dropped out from the study. Alternative, explicit, ways of addressing the issue of missing seizure data due to dropouts may be considered. (Kenward 2015) Two methods were chosen for minimal impact on variability of estimates as well as their simplicity.

It is assumed that the **planned duration** of T+M for Study 1 and Study 2 subjects is 14 weeks (98 days).

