### 10.3. Adverse Events

An AE is defined as any unfavorable and unintended sign (including an abnormal, clinically significant laboratory finding), symptom, or disease temporally associated with the use of a medicinal (investigational) product, whether or not considered related to the medicinal (investigational) product. The period of observation for adverse events extends from the time the subject gives informed consent until the end of the titration/transition period (Visit 13). For patients who continue into the open-label extension study, AEs of special interest will continue to be monitored for up to 6 months after the last dose of study medication.

A TEAE is defined as any AE that based on start date information occurs after the first intake of study treatment. Safety tables will present TEAE data by assigned treatment group through Visit 13. All other AEs occurring after enrollment and prior to the first administration of study treatment are defined as non-treatment emergent AEs (non-TEAEs).

AEs are categorized as related or unrelated. If the AE is thought to be definitely, probably or possibly related to study drug then it is to be categorized as related. Possibly or definitely unrelated is categorized as unrelated. Any missing relationship will be considered as "related."

The severity of AEs (whether nonserious or serious AEs) will be assessed by the investigator as follows:

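### The early-termination taper is set by randomised arm, not dose reached, so a 0.8 mg/kg/day subject who stops on Days 1-4 is stepped up from 0.2 to 0.4 mg/kg/day (minor)

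*SAP*

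**What the plan says.** The dosing rules are in section 3.3 of the Study 1 SAP (Tables 2 and 3) and section 2.7 of the Study 2 SAP (Tables 1 and 2). They agree in substance.

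- **Titration.** In the Study 2 wording, "the dose for each subject was titrated starting with a dose of ZX008 0.2 mg/kg/day (or placebo equivalent) BID". The 0.8 arm moves to 0.4 mg/kg/day on Day 5 and reaches 0.8 on Day 9.
- **Who is tapered.** Completers not entering the extension are tapered, and "subjects who discontinued from the study early were to be tapered off from study medication". The column headings of the taper tables count days from completion or from early termination.
- **Taper dose.** The rows are randomised groups. For the high dose, "subjects in the ZX008 0.8 mg/kg/day group decreased to a dose of ZX008 0.4 mg/kg/day BID" in step 1 (four days), then 0.2 mg/kg/day in step 2 (four days). For the low dose, "Subjects in the ZX008 0.2 mg/kg/day group decreased their dose to placebo on the first day of tapering".

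Neither SAP states a different taper for a subject who stops before reaching the target dose.

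**The concern.** The high-dose row of the taper table is a step down only for a subject already above 0.4 mg/kg/day. Someone in that arm who stops on Days 1-4 is on 0.2 mg/kg/day, so the first taper step is an increase. The period definitions (Study 1 SAP section 6.1.6; Study 2 SAP section 6.5) describe the taper as gradual, which does not fit this case.

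The subjects are children and young adults, and one possible reason for stopping in the first days of titration is poor tolerance. Followed literally, the rule gives such a subject more drug per day after stopping than before. The issue is patient safety and the correctness of a stated rule, not the efficacy inference.

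**Working it through.** **Inputs.** Titration dose t in the 0.8 arm: 0.2 (Days 1-4), 0.4 (Days 5-8) and 0.8 mg/kg/day (Day 9 on). Taper: 0.4 for 4 days, then 0.2 for 4 days. Daily cap: 30 mg. All are from the titration and taper tables and their notes.

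**The plan's own figure.** Taper length = 4 + 4 = 8 days, as stated.

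**Step 1 dose relative to the dose at stopping**, for body weight w in kg: min(0.4w, 30) / min(t·w, 30).

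| Stop in 0.8 arm | Ratio at step 1 |
|---|---|
| Days 1-4, w up to 75 kg | 0.4/0.2 = 2.0 (20 kg: 4 to 8 mg/day; 75 kg: 15 to 30 mg/day) |
| Days 1-4, 80 kg | 30/16 = 1.88 |
| Days 1-4, 100 kg | 30/20 = 1.5 |
| Days 1-4, 150 kg | 30/30 = 1.0 |
| Days 5-8 | 0.4/0.4 = 1.0 (up to 75 kg) |
| Day 9 on, w up to 37.5 kg | 0.4/0.8 = 0.5 |
| Day 9 on, 40, 60, 75 kg | 16/30 = 0.53; 24/30 = 0.8; 30/30 = 1.0 |

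The dose rises only after a Day 1-4 stop. Later stoppers are held or reduced.

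**Total drug after a Day 1-4 stop (up to 75 kg).** As written: 4 × 0.4 + 4 × 0.2 = 2.4 mg/kg, or 48 mg at 20 kg. Before stopping the subject has had at most 4 × 0.2 = 0.8 mg/kg. Schedules that never exceed 0.2 mg/kg/day give:
- placebo throughout: 0;
- 0.2 for four days, then placebo: 0.8 mg/kg;
- 0.2 for eight days: 1.6 mg/kg.

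The excess is therefore 2.4, 1.6 or 0.8 mg/kg (48, 32 or 16 mg at 20 kg).

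**How many subjects.** The Study 2 SAP (section 6.4) reports that "The rates of dropout in the pivotal trials was 7.56% (9/119) in Study 1"; 9/119 = 7.56% is confirmed. Arm and day of dropout are not given. Assuming equal arms and stops spread evenly over the 98 days of T+M:
- expected number = 9 × (1/3) × (4/98) = 0.12 per study;
- chance of at least one = 1 − (1 − 4/294)^9 = 0.116.

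If all nine had stopped within the 14 titration days, the expected number would be 9 × (1/3) × (4/14) = 0.86 with equal arms, or 9 × (4/14) = 2.57 if all were in the 0.8 arm. The documents support neither of these extremes.

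**Does other text remove the problem?** Footnote b to the schedule of assessments has these subjects "tapered off study medication over an up to 2-week period", which sets a duration and no dose. The transition rule carries an explicit limit: "Subjects who completed the Maintenance Period and were continuing into the open-label extension study were to be transitioned from double-blind study medication". The taper rule has no such limit and names early discontinuers.

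**The case against.** The strongest reply is that an SAP only summarises dosing, and that the handling of someone who stops in mid-titration belongs in the protocol and the IVR/IWR system, neither of which is available here. They may already deal with it, and editing the SAP alone changes no dose. The words used also show that a step down was intended. This limits what can be claimed: a reader might infer that subjects were actually dosed upward, and nothing in the documents shows that. It does not clear the rule, because both SAPs state a schedule, apply it to early termination, and get this case wrong.

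The exposure is also within the range under test. A subject who stayed on would have had 0.4 mg/kg/day from Day 5, and Days 5-12 would have totalled 4 × 0.4 + 4 × 0.8 = 4.8 mg/kg, twice the taper total. Taper bottles are dispensed at the end-of-study or early-termination visit, and the scheduled contacts between first dose and Day 15 are telephone calls. Both points stand and reduce the size of the concern.

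A reader might also infer that adverse events on these days will be counted under the assigned arm, with nothing to show the raised dose. Section 10.3 of the Study 2 SAP does say "Safety tables will present TEAE data by assigned treatment group through Visit 13". But the same section limits the TEAE and AESI summaries to T+M, and section 6.5 ends the double-blind period of an early discontinuer at the early-termination visit, before the taper begins. The Study 1 SAP has the same tension (sections 6.1.6, 6.4.1, 6.4.1.2 and 6.4.2). The plan is inconsistent on whether these events enter the TEAE tables, so no harm to the tabulation is established. Daily intake and drug accountability listings are already planned.

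It might be said that a change comes too late, since the Study 2 dosing text is in the past tense. That does not hold for the Study 1 SAP, whose section 6.9 says that both trials would go on enrolling about 120 further subjects.

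**Conclusion.** The point holds as a minor patient-safety error in the rule as written in both SAPs. A 0.8-arm subject stopping on Days 1-4 would have the daily dose doubled for four days at any weight up to 75 kg, with a smaller rise above that and none from 150 kg. Few subjects are affected and possibly none. The estimate of about 0.12 per study rests on equal arms, even timing and a dropout count like Study 1's.

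Two wider readings are not supported. Stopping on Days 5-8 is not an error, because the dose is held and then lowered. Nor is any efficacy result shown to depend on this: the taper falls after T+M, the period of the primary analysis, and taper data are kept out of the efficacy endpoints unless specified. The Maintenance-only repeat borrows Transition data for subjects who never reached Maintenance; whether that was meant to include taper days is unclear, and nothing is claimed from it.

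**What to change.** For subjects still to be dosed, add to the taper text that no step may exceed the dose last taken. Spell out the result, since the cap alone would also allow 0.2 mg/kg/day to continue: a 0.8-arm subject stopping on Days 1-4 goes to placebo for both steps, as the 0.2 arm already does. All later stoppers keep 0.4 then 0.2 as written. The blinded 8-day, two-bottle schedule stays. The same change is needed in the protocol and the IVR/IWR system if they carry the same rule.

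For subjects already dosed, leave the dosing description as it is. Flag in Listing 16.2.5.1 (daily IMP intake, already planned in both SAPs) any 0.8-arm subject who stopped on Days 1-4, with the taper dose given. That would settle whether the case occurred.

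The cost is a short addition to the taper text, a small protocol and IVR/IWR change where dosing continues, and one flag in an existing listing with no new data collection.
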